# **1.2.3** Assessment of Potential Risks and Benefits

APX001 is a broad-spectrum antifungal agent, available in both IV and PO formulations, with wide-tissue distribution, including the eye and central nervous system. APX001 has a differentiated safety and DDI profile compared to SOC antifungal therapy. Patients with limited treatment options will be included in this investigational study if they have an invasive infection with *Aspergillus* or a rare mold, and there is a potential advantage of receiving treatment with APX001 compared to the current SOC.

Patients participating in this clinical study will receive more intense health monitoring as detailed in the schedule of procedures.

### 2 STUDY OBJECTIVES

### 2.1 **Primary Objective**

The primary objective of this proof-of-concept study is to evaluate the safety and efficacy of APX001 for the treatment of adult patients aged 18 years and above with IMIs caused by *Aspergillus* spp. or rare molds (eg, *Scedosporium* spp., *Fusarium* spp., and Mucorales fungi), who have limited antifungal treatment options.

### 2.2 Secondary Objectives

The secondary objectives of this study are to:

- Evaluate global response at End of Study Treatment (EOST)
- Evaluate safety parameters of APX001
- Evaluate PK parameters of APX001

### **3 STUDY DESCRIPTION**

### 3.1 Summary of Study Design

This is a Phase 2, multicenter, open-label, parallel-group, non-comparative study to evaluate the safety and efficacy of APX001 for the treatment of IMIs caused by *Aspergillus* spp. or rare molds (eg, *Scedosporium* spp., *Fusarium* spp., and Mucorales fungi). Patients 18 years of age or older will undergo Screening procedures for up to 5 days, following which eligible patients will participate in the study drug Treatment Period for up to 6 weeks, with a Follow-Up Visit 4 weeks after EOST, and a Follow-Up Phone Call 12 weeks after Day 1 (Day 84). The total duration of a patient's participation in the study will be approximately 12 weeks, inclusive of the follow-up telephone call required on Day 84. Patients who require treatment for longer than 6 weeks can be switched to other licensed antifungal therapy (OLAT) at the discretion of the Investigator and in consultation with the Medical Monitor if the situation allows.

This study will be conducted at up to 40 global sites.

A complete schedule of procedures for the study is found in APPENDIX A.

Figure 1 presents a schematic for the study.

# Figure 1. Study Schematic

BID = twice daily; EOST = End of Study Treatment; IV = intravenous(ly); PO = oral(ly); QD = once daily.

This study will consist of CCI parallel cohorts. Cohort A will enroll up to 40 patients, Each cohort has a single treatment arm consisting of a loading dose of 1000 mg APX001, administered over 3 hours by IV infusion twice daily (BID) within the first 24 hours after initiation of the first infusion. On Days 2 and 3, 600 mg APX001 will be administered over 3 hours by IV infusion once daily (QD). From Day 4 through EOST, the IV dose remains 600 mg APX001 administered over 3 hours by IV infusion QD, or patients may be switched to PO administration of 800 mg APX001 QD. Antiemetics (preferably a 5-HT3 antagonist such as ondansetron or granisetron) should be administered in patients who develop nausea and/or vomiting associated with APX001 administration (both IV and oral), and oral APX001 may be given with food. Additionally, prophylactic antiemetics, (preferably a 5-HT3 antagonist such as ondansetron or granisetron) may be administered prior to dosing (both IV and oral) in patients considered at higher risk of gastrointestinal intolerance. The decision to switch from IV to PO APX001 will be based on the Investigator's discretion and can be done on any day from Day 4 onwards. Patients will remain hospitalized for at least 2 days following the initial switch from IV to PO so that their tolerance to the oral medication may be evaluated and treated as necessary. Patients may be switched between IV and PO as needed. Oral APX001 may be given as an outpatient.

Administration of APX001 should not continue for longer than 6 weeks (inclusive of the loading dose [Day 1]). If an Investigator documents an improvement or resolution in clinical signs and symptoms prior to 6 weeks, eg, if follow-up imaging (as applicable) shows improvement; or a

mycological response (if amenable to repeat sampling) is observed, the Investigator may choose to discontinue dosing. Patients will be requested to return for an EOST and Follow-Up Visit and to agree to a Follow-Up Phone Call.

Table 1 describes dosing for the study.

Radiological assessments (including computed tomography [CT] scans of the chest, sinuses, and/or abdomen) will be performed during Screening (SOC scans within 3 days of Screening will be accepted as long as the scans can be provided to the central reader). Computed tomography scans of the chest, sinuses, and/or abdomen will be repeated on Day 14 and at EOST, and if clinically indicated on Days 7, 21, 28, 35, and 42; at the Follow-Up Visit; and at the E/T Visit (if applicable).

Samples for fungal cultures (eg, from BAL fluid, sputum, bronchial brush, sinus aspirate, tracheal aspirate) will be collected and processed for culture and susceptibility by the local laboratory at Screening, and as clinically indicated at any visit from Day 1 (Baseline) through EOST, at the Follow-Up Visit, and at the E/T Visit (if applicable). Screening samples for fungal cultures to determine eligibility may have been collected as SOC within 120 hours prior to initial dosing. All fungal isolates cultured at the local laboratory will be sent to the central mycology reference laboratory for confirmation of identification and susceptibility testing.

Bronchoalveolar lavage samples will be collected per SOC for culture at the local laboratory and **CCI** testing at the central laboratory as clinically indicated at any visit from Screening throughout the study.

The safety and tolerability of APX001 will be evaluated through physical examination findings, clinical signs and symptoms, vital signs, changes in clinical laboratory tests, 12-lead ECGs, any other exploration, and monitoring of adverse events and concomitant medications or procedures.

# **3.2** Study Indication

APX001 is indicated for the treatment of patients with IMIs caused by *Aspergillus* spp. or rare molds.

# 4 SELECTION AND WITHDRAWAL OF PATIENTS

# 4.1 Inclusion Criteria

This study will enroll male and female patients aged 18 years and above with a confirmed diagnosis of invasive aspergillosis or invasive rare mold infection. Patients will have limited or no treatment options due to documented/anticipated resistance, contraindication, intolerance, or lack of clinical response to SOC antifungal therapy, as advocated by the relevant regional/country treatment guidelines. The study will enroll CCI cohorts, Cohort A CCI Up to 40 patients will be enrolled in Cohort A, and these patients will have an IMI which was diagnosed according to the EORTC/MSGERC criteria.

Patients must meet all of the following criteria to be eligible for study entry:

- 1. Males or females, 18 years or older.
- 2. Patients with IMI caused by *Aspergillus* spp. Patients who present with IMI due to other filamentous fungi (eg, *Scedosporium* spp., *Fusarium* spp., and Mucorales fungi such as *Mucor* spp. or *Rhizopus* spp.) may also be enrolled.
  - Cohort A: Diagnosis of proven or probable IMI will be defined in accordance with the Revision and Update of the Consensus Definitions of Invasive Fungal Disease from the EORTC/MSGERC (Donnelly et al., 2019) (see APPENDIX D and APPENDIX E).

- 3. Have limited or no treatment options due to documented or anticipated resistance, contraindication, intolerance, or lack of clinical response to SOC antifungal therapy, as advocated by the relevant regional/country treatment guidelines.
- 4. Patients where the Investigator considers that there is a potential advantage of using APX001 over current SOC (eg, broad spectrum of activity, activity against resistant mold pathogens, IV and PO formulations, favorable DDI profile, favorable hepatic and renal safety profile, wide tissue distribution including brain), and/or where SOC antifungal therapy carries significant risk of toxicity or treatment failure (eg, emergence of IMI during antifungal prophylaxis, DDI risk, safety/toxicity risk, site of infection not accessible by SOC).
- 5. Female patients of nonchildbearing potential must be 1 of the following:
  - Surgically sterile (hysterectomy, bilateral tubal ligation, bilateral salpingectomy, and/or bilateral oophorectomy).
  - Postmenopausal (amenorrhea for >12 months without an alternative medical cause).
- 6. Females of childbearing potential (ie, not postmenopausal or surgically sterilized) must have a negative urine or serum pregnancy test result within 96 hours prior to Baseline (ie, predose on Day 1). Participating females of childbearing potential with male partners, and males with female partner(s) of childbearing potential, must agree to use 2 forms of contraception, 1 of which must be highly effective and the other an acceptable barrier method (male or female condom), throughout the duration of the study and for 90 days following the last study drug administration. Highly effective methods of contraception include the following:
  - Combined (estrogen and progestogen containing) hormonal contraception associated with inhibition of ovulation (PO, intravaginal, or transdermal), progestogen-only hormonal contraception associated with inhibition of ovulation (PO, injectable, or implantable), intrauterine device, or intrauterine hormone-releasing system.
  - Bilateral tubal occlusion or vasectomized partner.

**Note:** A vasectomized partner is a highly effective method of contraception, provided that the male partner is the sole sexual partner of the study patient who is a female of childbearing potential and that the vasectomized partner has received medical assessment of surgical success.

• Sexual abstinence.

**Note:** True abstinence, when in line with the preferred and usual lifestyle of the patient, is considered a highly effective method only if defined as refraining from heterosexual intercourse during the entire period of risk associated with the study drug treatment. Periodic abstinence (eg, calendar, ovulation, symptothermal, postovulation methods) and withdrawal are not acceptable methods of contraception.

7. Male patients must agree to abstain from sperm donation and use condoms with spermicide during sexual intercourse between Screening and at least 90 days after administration of the last dose of study drug. Male patients must ensure nonpregnant female partner(s) of childbearing potential comply with the contraception requirements in Inclusion Criterion 6.

- 8. Patients must be willing to participate in the study, to give written informed consent, and to comply with the study restrictions; where permitted by local regulations, written informed consent from a legal authorized representative (LAR) will be obtained for patients who are unable to give consent.
- 9. CCI

# 4.2 Exclusion Criteria

Patients who meet any of the following criteria will not be eligible for the study:

- 1. Refractory hematologic malignancy with no potential to respond to additional chemotherapy.
- 2. Chronic aspergillosis, aspergilloma, or allergic bronchopulmonary aspergillosis.
- 3. Treatment with systemic (PO, IV, or inhaled) antifungal therapy with a mold-active azole or polyene for ≥120 hours immediately before initial dosing.

**Note**: An exception is antifungal prophylaxis, for which there is no restriction on duration but must be stopped upon commencement of treatment with APX001.

Additionally, patients with invasive fungal infection caused by a mold with documented resistance to or lack of coverage by the prior SOC in question, as well as patients with polyene-induced renal toxicity or those who have received empirical treatment with echinocandins may have received >120 hours prior treatment and remain eligible for the study. These patients must be discussed with the Medical Monitor prior to enrollment, and prior treatment in this case should not exceed >168 hours.

- 4. Evidence of significant hepatic dysfunction, defined as any of the following:
  - Total bilirubin >3 × the upper limit of normal (ULN) unless isolated hyperbilirubinemia or due to documented Gilbert's disease.
  - Alanine transaminase or aspartate transaminase  $\geq 5 \times ULN$ .
  - Severe or moderate hepatic impairment (Child-Pugh Score >6 points) at any time during 2 weeks prior to dosing. The Child-Pugh score of > 6 is applicable only to patients with hepatic dysfunction and cirrhosis.
- 5. Ongoing medical history of neurological disorders including abnormal movements or seizures. **Note:** A current CNS mold infection as well as a stable history of peripheral neuropathy will not be considered exclusionary.
- 6. Patient receiving palliative care only.
- 7. Known hypersensitivity or other serious reaction to APX001 or any ingredient of APX001.
- 8. Patient is lactating and/or pregnant or intending to be pregnant during the duration of the study.

9. Investigational drug administered within 30 days or 5 terminal half-lives prior to study drug dosing (whichever is longer).

**Note**: Participation in research protocols for approved agents for the treatment of an underlying condition is permitted.

- 10. Prior participation in this study or any previous study of APX001.
- 11. Concomitant use of medication that is a strong inducer (ie, rifampin, carbamazepine, phenytoin, rifabutin, efavirenz, nevirapine, phenobarbital, modafinil, St. John's Wort, enzalutamide) of CYP enzymes.
- 12. Any other condition or laboratory abnormality that, in the opinion of the Investigator or the Sponsor, would put the patient at unacceptable risk for participation in the study or may interfere with the assessments included in the study.
- 13. Patients on mechanical ventilation
- 14. Cohort A only: Suspected or confirmed COVID-19 or Influenza A/B infection.
- 15. Patients with severe renal impairment as determined by estimated glomerular filtration rate (eGFR) <30 mL/min /1.173 m^2 calculated by CKD-EPI, including patients on dialysis
- 16. Patients with a Karnofsky Performance Status  $\leq$  30 at screening

# 4.3 Withdrawal Criteria

Study drug dosing must be discontinued for any of the following reasons:

- The patient withdraws consent or requests discontinuation from the study for any reason
- Occurrence of any medical condition or circumstance that exposes the patient to substantial risk and/or does not allow the patient to adhere to the requirements of the protocol
- Occurrence of drug-induced liver injury (DILI) [APPENDIX G]
- Any SAE, clinically significant adverse event, severe laboratory abnormality, intercurrent illness, or other medical condition which indicates to the Investigator that continued participation is not in the best interest of the patient
- Pregnancy
- Requirement of prohibited concomitant medication (eg, systemic antifungal therapy)
- Patient failure to comply with protocol requirements or study-related procedures
- Termination of the study by the Sponsor or the regulatory authority

If a patient must be discontinued from study drug administration for any of the above criteria, the patient will still be encouraged to continue visits and assessments necessary for appropriate safety follow-up.

If a patient withdraws prematurely from the study due to any of the above criteria or for any other reason, study staff should make every effort to contact the Sponsor prior to discontinuation, if possible, and to complete the full panel of assessments scheduled for the E/T Visit. The reason for patient withdrawal must be documented in the electronic Case Report Form (eCRF).

In the case of patients lost to follow-up, attempts to contact the patient must be made and documented in the patient's medical records.

Withdrawn patients will not be replaced.

# 4.4 Discontinuation Rules

# 4.4.1 Study Discontinuation Rules

At any time, the independent Data and Safety Monitoring Board (DSMB) may temporarily suspend enrollment until any significant safety concerns are resolved or terminate the study to ensure patient safety, if in the opinion of the DSMB, further dosing would pose an inappropriate safety risk. Guidelines for what constitutes inappropriate safety risks are described in the DSMB Charter.

Additionally, the study may be discontinued for any of the following reasons: 5 or more patients in the study (cumulative) experience the same Grade 2 (or higher) related adverse event (laboratory or clinical) which is coded in the same high-level group term per the Medical Dictionary for Regulatory Activities coding, throughout the duration of the study; lack of study drug availability; inability to enroll the study; or decision by a regulatory authority or the Sponsor.

# 4.4.2 Patient Discontinuation Rules

Study treatment for an individual patient may be discontinued for lack of clinical and/or microbiological response, any adverse event, SAE, laboratory abnormality, or intercurrent illness which, in the opinion of the Investigator, indicates that continued dosing in the study is not in the best interest of the patient. Whenever feasible, the Investigator should discuss the patient situation with the Medical Monitor prior to discontinuation of the patient.

A patient who has discontinued study drug administration will still be encouraged to continue visits and assessments necessary for appropriate safety follow-up, and to complete the full panel of assessments scheduled for the E/T Visit. The reason for patient withdrawal must be documented in the eCRF.

In the case of patients lost to follow-up, attempts to contact the patient must be made and documented in the patient's medical records.

Withdrawn patients will not be replaced.

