#### 6.4 End of Study Treatment (+2 Days)

The EOST should occur as soon as possible following completion of APX001 dosing and within 2 days of last dose. The following procedures will be performed at EOST (+2 days):

- Record Investigator assessment of global response.
- Assess survival status.
- Perform urine or serum pregnancy test on women of childbearing potential only.
- Perform a complete physical examination including assessment of general appearance, skin, eyes, heart, chest, abdomen, and a neurological examination and measure weight.
- Assess clinical signs and symptoms.
- Record vital signs, including temperature, blood pressure, heart rate, respiratory rate, and oxygen saturation.
- Perform 12-lead ECG in triplicate.
- Perform clinical laboratory assessments (serum chemistry, hematology [including CBC with differential], coagulation [including PT/INR], and urinalysis).
- Perform CT scan.
- Collect serum samples for analysis of CCI and C
- Collect samples for fungal cultures (eg, from BAL fluid, sputum, bronchial brush, sinus aspirate, tracheal aspirate) as clinically indicated.

- Collect BAL samples per SOC for culture and CCI testing as clinically indicated.
- Collect plasma PK samples at any time in clinic.
- Record concomitant medications.
- Assess adverse events.
- Review accountability for all returned study drug.

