#### 6.7 Early Termination Visit and Withdrawal Procedures

For patients who are withdrawn from the study prior to completion, the following procedures will be performed at an E/T Visit:

- Perform urine or serum pregnancy test on women of childbearing potential only.
- Perform a complete physical examination including assessment of general appearance, skin, eyes, heart, chest, abdomen, and a neurological examination and measure weight.
- Assess clinical signs and symptoms.
- Record vital signs, including temperature, blood pressure, heart rate, respiratory rate, and oxygen saturation.
- Perform 12-lead ECG in triplicate.
- Perform clinical laboratory assessments (serum chemistry, hematology [including CBC with differential], coagulation [including PT/INR], and urinalysis).
- Perform CT scan if clinically indicated.
- Collect serum samples for analysis of CCI and C.
- Collect samples for fungal cultures (eg, from BAL fluid, sputum, bronchial brush, sinus aspirate, tracheal aspirate) as clinically indicated.
- Collect BAL samples per SOC for culture and CCI testing as clinically indicated.
- Collect plasma PK samples at any time in clinic.
- Record concomitant medications.
- Assess adverse events.

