#### 9.2.4 Data Review Committee

A DRC comprised of infectious disease experts will adjudicate the diagnosis of IMI at enrollment. This committee will also provide systematic assessment for clinical, mycological, radiological, and global responses at EOST and at the E/T Visit (if applicable).

Global responses will be classified as complete or partial response (categorized as treatment success), stable response, progression of disease, or death (categorized as treatment failure) according to prespecified criteria (APPENDIX G). Guidelines for the DRC are described in the DRC Charter.

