3.2. Secondary Efficacy Endpoint(s) Assessed by DRC

The secondary efficacy parameter for this study is Global Response at EOST/ET. Global response will be classified as follows according to prespecified criteria, as determined by the DRC (Guidelines for the DRC are described in the DRC Charter):

- Complete Response: Survival within the prespecified period of observation, resolution of all attributable symptoms and signs of disease and radiological abnormalities, and mycological evidence of eradication of disease).
- Partial Response: Survival within the prespecified period of observation, improvement in attributable symptoms and signs of disease and radiological abnormalities, and evidence of clearance of cultures or reduction of fungal burden, as assessed by a quantitative and validated laboratory marker categorized as treatment success.
- Stable Response: Survival within the prespecified period of observation and minor or no improvement in fungal disease, but no evidence of progression, as determined based on a composite of clinical, radiological, and mycological criteria, progression of disease, or death (categorized as treatment failure).
- Progression of fungal disease: Evidence of progressive fungal disease based on a composite of clinical, radiological, and mycological criteria.

• Death: Death during the prespecified period of evaluation, regardless of attribution. If any patient has missing global response at EOST, it will be presented as 'Indeterminate' in the summary.

Treatment outcomes for Global Response based on DRC assessment at EOST are defined as follows:

- Treatment success: Complete response or partial response.
- Treatment failure: Stable response, progression of fungal disease and death.

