6.3. Secondary Endpoint(s)

Global response at EOST. Global responses will be classified as complete or partial response (categorized as treatment success), stable response, progression of fungal disease, or death (categorized as treatment failure) by the Investigator and adjudicated by the DRC.

Number and percentage of patients in the mITT Populations with global responses at EOST as determined by the DRC will be tabulated for Cohort A. Two-sided 80% exact binomial CIs of the treatment success rate will be presented for Cohort A only.

Global response will also be summarized descriptively as, complete response, partial response, stable response, progression of fungal disease, death at EOST, ET and EOST/ET (LOCF).

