Appendix 1. Summary of Efficacy Analyses

Endpoint	Analysis Type	Population	Data Inclusion and Rules for Handling Intercurrent Events and Missing Data	Analysis Model
Primary endpoint: Mortality rate at Day 42.	Primary	mITT	All observed data.	Cohort A: One-sided exact binomial test at the alpha = 0.1 level of significance:
Secondary Endpoint: Global response at EOST	Secondary	mITT	All observed data	Cohort A: Two-sided 80% exact binomial CI
Clinical responses	Other	mITT	All observed data	Cohort A: Two-sided 80% exact binomial CI
Radiological response	Other	mITT	All observed data	Cohort A: Two-sided 80% exact binomial CI
Mycological response	Other	mITT	All observed data	Cohort A: Two-sided 80% exact binomial CI
CCI				

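### The protocol contradicts itself on which visit follows early stopping of drug, and E/T collects less response data than EOST, so the data behind global response can differ by reason for stopping

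*Protocol*

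**What the plan says.** **Stopping for non-response or toxicity.** Protocol 4.4.2 covers these patients: "Study treatment for an individual patient may be discontinued for lack of clinical and/or microbiological response, any adverse event, SAE, laboratory abnormality, or intercurrent illness". They are encouraged to continue visits needed for safety follow-up "and to complete the full panel of assessments scheduled for the E/T Visit". No other panel is named for them.

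**Stopping for improvement.** Protocol 3.1, 5.5.3 and Appendix A note a ask these patients to return for EOST.

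**What each visit collects.** EOST (6.4) includes "Record Investigator assessment of global response", survival status and an unconditional CT. E/T (6.7) lists neither of the first two, and its imaging entry is "Perform CT scan if clinically indicated". The schedule in Appendix A agrees: the global-response and survival rows are blank under E/T.

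**When each visit applies.** Section 6.4 and Appendix A note d set EOST within 2 days of the last dose and name no reason for stopping; SAP Appendix 2.1 also counts from the last treatment date. Sections 4.3 and 6.7 attach E/T to withdrawal from the study. Section 4.4.2 attaches it to stopping drug.

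**What the analysis uses.** The DRC rates response at both visits (Protocol 9.2.4: "This committee will also provide systematic assessment for clinical, mycological, radiological, and global responses at EOST and at the E/T Visit (if applicable"). SAP 3.2 states: "The secondary efficacy parameter for this study is Global Response at EOST/ET". SAP 6.3 has responses classified by the Investigator and adjudicated by the DRC, and tabulates EOST, ET and a combined EOST/ET (LOCF).

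**Missing responses.** SAP 5.4 keeps patients with missing outcomes in the denominator and labels a missing response as missing. SAP 3.2 labels it Indeterminate. The Appendix 1 entry is "All observed data".

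**The concern.** The reason a patient stops drug is related to the outcome being rated. If stopping for improvement leads to a visit with imaging and an Investigator rating, and stopping for failure or toxicity leads to one without them, the completeness of the response data depends on how the patient is doing. Under Appendix G, complete and partial response both need radiological change, and stable response and progression are composites that include radiology. The DRC may therefore have to rate E/T patients without imaging that its criteria use. Global response at EOST is the first-listed secondary objective, and about 24 mITT patients are expected, so each patient carries 1/24 = 4.2 percentage points.

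**Working it through.** **1. The plan's own figures.** The documents give no planned value for global response. The expected mITT size is 40 × 0.60 = 24. The stated power above 90% belongs to the mortality test. It reproduces: rejecting at 7 or fewer deaths of 24 gives exact one-sided alpha 0.086 under 45% mortality and power 0.911 under 20%. It does not depend on this point.

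**2. The two visits compared.**

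| Item | EOST (6.4) | E/T (6.7, Appendix A) |
|---|---|---|
| Investigator global response | yes | not listed |
| CT | required | if clinically indicated |
| Survival status | yes | not listed |
| Signs and symptoms, complete examination, serum markers | yes | yes |
| Cultures, BAL | as clinically indicated | as clinically indicated |

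The differences that matter for response are the first two rows. An Investigator global response is scheduled only at Day 42 and EOST.

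**3. Routing.** Under 4.4.2 alone, a patient stopped for non-response gets the E/T panel. Under 6.4, the same patient gets EOST within 2 days of the last dose. Both readings have textual support, and nothing states which prevails.

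**4. Effect on the success rate.** The documents give neither a success count nor a number of E/T patients. Assume 12 successes among 24 mITT patients, and m further patients with no usable response. Intervals are exact (Clopper-Pearson), two-sided 80%, as SAP 6.3 specifies.

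- SAP 5.4 rule (missing stays in the denominator): 12/24 = 50.0% (35.3 to 64.7%) for any m.
- Observed-data denominator, 12/(24 − m):
  - m = 2: 12/22 = 54.5% (38.9 to 69.5%)
  - m = 4: 12/20 = 60.0% (43.3 to 75.1%)
  - m = 6: 12/18 = 66.7% (48.8 to 81.5%)

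**5. Effect in the other direction.** Take m = 4 under SAP 5.4. If all four are true failures, the reported 50.0% is correct, but four failures (4/24 = 16.7%) are tabulated as Indeterminate or missing. If two of the four were responders who stopped for toxicity, the true rate is (12 + 2)/24 = 58.3%, and the reported 50.0% is too low.

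**The case against.** The strongest reply is that this is a conflict of visit wording, not a missing endpoint. Much of that stands.

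- A reader might infer that E/T has no response assessment. The documents do not support this. The secondary endpoint is the DRC's rating, and both documents provide for it at E/T. What is absent is the Investigator's rating and required imaging. E/T still collects signs and symptoms, an examination and serum markers, and a Day 14 CT is required of patients still attending then. The DRC Charter is not among the documents, so it cannot be shown that the DRC would be unable to classify these patients.
- A reader might infer that early stoppers always miss EOST. Sections 4.3, 6.4 and 6.7 permit EOST after any last dose, and 4.4.2 does not say that E/T replaces it.
- A reader might infer that the success rate is inflated. SAP 5.4 places missing outcomes in the denominator, so unassessed failures cannot raise it. Since success needs radiological improvement, a missing CT blocks a success more readily than a failure. The Appendix 1 wording says nothing explicit about the denominator.
- A reader might infer that the missing survival item threatens the primary endpoint. Section 7.1 seeks Day 42 survival for all dosed patients whatever their treatment status, unless consent is withdrawn.
- A reader might infer that LOCF has nothing to carry forward, or that a planned Investigator ET table cannot be filled. The combined EOST/ET summary may simply use the DRC's ET rating where EOST is absent. SAP 3.2.1.4 defines the Investigator's rating at EOST only.

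The reply does not remove the contradiction between 4.4.2 and the other sections. Nor does it explain why response data should be thinner at a visit where the DRC must rate radiological and global response.

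**Conclusion.** The point holds in limited form. The protocol gives two routes after early stopping. One of them collects less response data, and 4.4.2 applies it to patients stopped for non-response, toxicity or intercurrent illness. Response data can therefore differ by reason for stopping.

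The size is unknown, because the number of patients who would have only E/T data is not given. Under SAP 5.4 the cost is mislabelled failures and possible undercounting of responders. Under an observed-data reading of Appendix 1, the assumed 50% would become 55 to 67% for 2 to 6 unassessed patients. A bias in the drug's favour is not established, and the primary mortality test is untouched. The correction should be made: it is small, and it protects the first-listed secondary objective.

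**What to change.** 1. **Protocol 4.3, 4.4.2, 6.4, 6.7 and Appendix A.** Reconcile them so that a patient who stops drug for any reason but stays in the study completes the EOST assessments, with E/T reserved for withdrawal from the study.
2. **Protocol 6.7 and the E/T column of Appendix A.** Add the Investigator global response, and bring the collection of response data into line with EOST, because the DRC must rate response there.
3. **SAP 3.2, 6.3 and Appendix 1.** Align them with SAP 5.4: an mITT patient with no evaluable EOST or E/T response stays in the denominator, counts as not a success, and is shown under one label.

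The cost is one more form entry at an existing visit and, for some early stoppers, the CT already scheduled at EOST. The reported success rate may be slightly lower than under an observed-data denominator. No sample size or power figure changes.
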